13.1.7 Breaking of the Study Blind by the Investigator

The blind should be broken by the Investigator only in the case of emergency and if knowledge of the administered compound is deemed necessary for the medical treatment of the subject. Should it be necessary to break the blind, the Investigator will be able to do this using the IWRS. If possible, the Sponsor

should be notified before the study drug blind is broken. If the blind is broken the Investigator must immediately notify the CRO and provide the subject's number. The reason for breaking the blind should be noted on the Adverse Event (or Serious Adverse Event) section of the Case Report Form. Newron will inform the Safety Monitoring Board of the unblinding.

13.1.8 Pregnancy

Females of childbearing potential who are not using a contraception method judged to be adequate by their Health Care Provider, will not be eligible for the study. [*UK only*: Adequate contraception is defined as the use of a hormonal contraceptive or an Intra Uterine Device (IUD), preferably in conjunction with a spermicidal substance. Appropriate guidelines for use of the specific contraceptive should be followed. For patients whose illness is severe, i.e. advanced stage of physical and mental incapacitation, and are sexually inactive, the caregiver and the healthcare provider should discuss the most appropriate option, including abstinence. Adequate contraception should be continued until 4 weeks after stopping study medication.

As a further precaution, a serum pregnancy test will be performed at screening and baseline for all post-pubertal females. In addition, a serum pregnancy test will be performed at Weeks 24, 48, 72, 96, 120, 144, 168 and 192 (or at early discontinuation) for post-pubertal females; additional serum pregnancy tests may be performed, based on local requirements.

If a patient becomes pregnant during the study, she will be discontinued from the study immediately. The Investigator must report all pregnancies, within 24 hours of notification by the patient, to the CRO by email or by fax using the Pregnancy Reporting form. The timelines and other reporting requirements are the same as for a Serious AE. The patient (or her parent or legal guardian/representative) should be instructed to notify the Investigator within 24 hours if it is determined, after completion of the study, that the patient has become pregnant, either during the treatment phase of the study or within 30 days of completing the study. Whenever possible, a pregnancy should be followed to term and for 1 year after delivery of the baby, and any premature terminations reported. The status of the mother and child should be reported to the CRO or NEWRON within 24 hours after delivery, and one year later.

13.2 Safety Monitoring Board

An Independent Safety Monitoring Board (ISMB) will be established by Newron to review the safety of all patients enrolled in the Sarizotan 001/II/2015 study. It will be made up of at least 3 voting members. All of these members will have taken part in other international safety monitoring boards. [name], Newron's Chief Medical Officer, will serve as the Sponsor's primary contact for the ISMB.

The ISMB will review data from all patients enrolled at specified intervals throughout the trial. The ISMB will receive unblinded data; however, the blind will be maintained to the investigators, Sponsor, and CRO until after the final analysis has been completed. The CRO and Sponsor will compile subject data by treatment group and provide to the ISMB. The ISMB will have access to safety data, including adverse events, dropouts, SAEs, clinically significant abnormal laboratory tests, vital signs and ECGs, The ISMB will be regularly notified of the occurrence of any fatal/life threatening event within 24 hours and other serious adverse events within 72 hours. The ISMB will also receive detailed information on any adverse dropouts occurring in the study.

The ISMB is empowered to review all of the safety data on an ongoing basis, with special emphasis on serious AEs and deaths, in addition to the standard safety parameters. Based on their review of the safety data the ISMB will make a recommendation to Newron to (a) amend the ongoing study (e.g., increase safety monitoring), (b) terminate the study (e.g., the sarizotan safety profile is unacceptable), or (c) continue the

Amend. 1, 19Jan2016; Amend. 2, 18May2016; Amend. 3, 21Oct2016; Amend. 4, 03Mar2017; Amend. 5, 29Mar2017; Amend. 6, 13Apr2017; Amend. 7, 02Oct2017; Amend. 8, 02Nov2017; Amend. 9, 11Feb2018; Amend. 10, 29Nov2018; Amend. 13, 10Dec2019; Amendment 14, 17 March 2020, Clean, Final

study as designed. The current study protocol will not be amended or changed (this includes the study design and entry criteria) unless mandated by the emerging (unblinded) safety profile of sarizotan.

Details of the ISMB charter (separate document) will be submitted to regulatory authorities, and will be available to IECs/IRBs upon request.

14 SUBJECT COMPLETION AND DISCONTINUATION

A subject will be considered to have completed the initial randomized treatment period of the study if the subject returns for the final visit at Week 24. ‘Discontinuation’ will refer to any subject who does not complete the full 24 weeks (168 ± 7 days) of the initial treatment period of the study. A subject will be considered to have completed the initial 24-week open-label extension treatment period of the study if the subject returns for the final visit at Week 48 (336 ± 14 days). A subject will be considered to have completed Part 1 of the additional extension treatment period of the study if the subject returns for the final visit at Week 96 (672 ± 14 days). A subject will be considered to have completed Part 2 of the additional extension treatment period of the study if the subject returns for the final visit at Week 144 (1008 ± 28 days). A subject will be considered to have completed Part 3 of the additional extension treatment period of the study if the subject returns for the final visit at Week 192 (1344 ± 28 days). The end of the study for an individual patient is defined as completion of the Week 48 evaluation (for patients not entering the additional extension period), the Week 96 evaluation (end of Part 1; for patients not continuing open-label treatment after Week 96), the Week 144 evaluation (for patients enrolled in Part 2 of the open-label extension), or the Week 192 evaluation (for patients enrolled in Part 3 of the open-label extension), and the Safety Follow-up assessment 2 weeks after the last dose of study medication.

In the absence of a medical contraindication or significant protocol deviation, every effort should be made by the investigator to keep the subject in the study; however, should the subject be withdrawn, all efforts will be made to complete and report the observations as thoroughly as possible, including post-treatment evaluation at the time of the subject’s withdrawal, with an explanation of why the subject is withdrawing from the study.

The criteria for discharging a subject from the study prior to a post-study examination are listed below. The reason and time of all discontinuations will be specified on the ‘final overall assessment’ form.

A subject may be withdrawn from the study participation if:

- Any hypersensitivity or allergic reaction, clearly linked to the study medication, has occurred;
- Subject experiences an AE sufficiently severe, in the opinion of the investigator, that contraindicates continuing in the study;
- Subject wishes to withdraw (e.g. subject refuses to have any more PK blood samples taken; in this instance a specific reason must be recorded by the investigator)
- A subject is afflicted with a systemic illness, unrelated to the study medication but during the study period, for which a concomitant medication is required;
- A major protocol deviation has occurred, e.g., the subject failed to meet protocol entry criteria or did not adhere to protocol requirements, and continued participation poses an unnecessary risk to the subject’s health.
- The subject is lost to follow-up, i.e., the subject did not return to the clinic, and attempts to contact the subject were unsuccessful. Attempts to contact the subject must be documented.
- The Sponsor, Institutional Review Board / Independent Ethics Committee (IRB/IEC), or regulatory agency terminates the study.

Dropouts will not be replaced.

14.1 Procedures for handling withdrawals

The Investigator may terminate a subject’s study participation at any time during the study if a subject meets the study termination criteria described in [Section 14](#). In addition, a subject may discontinue his/her participation without giving a reason at any time during the study. Should a subject’s participation be

Amend. 1, 19Jan2016; Amend. 2, 18May2016; Amend. 3, 21Oct2016; Amend. 4, 03Mar2017; Amend. 5, 29Mar2017; Amend. 6, 13Apr2017; Amend. 7, 02Oct2017; Amend. 8, 02Nov2017; Amend. 9, 11Feb2018; Amend. 10, 29Nov2018; Amend. 13, 10Dec2019; Amendment 14, 17 March 2020, Clean, Final

discontinued, the primary reason for termination must be recorded. If a subject is withdrawn from the study after receiving a dose of study medication, he/she will not be replaced. An attempt should be made to perform all final (Week 24 [double-blind period], Week 48 [initial 24-week open-label extension period], Week 96 [Part 1 of additional open-label extension period], Week 144 [Part 2 of additional open-label extension period], or Week 192 [Part 3 of additional open-label extension period]) assessments on the subject, and to follow up on any safety issues until resolution. Subjects who discontinue prematurely, as well as those subjects completing the study, should return to the clinic for a Safety Follow-up assessment 2 weeks after the last dose of study medication, and must be followed up for 30 days after the last dose of study medication regarding the occurrence of Serious Adverse Events.

15 PHARMACOKINETIC AND STATISTICAL METHODS

15.1 Pharmacokinetics and Determinants of Pharmacokinetic Variability

The concentrations of sarizotan in plasma samples will be determined using a validated LC-MS/MS method (see [Section 11.2](#)).

Appropriate pharmacokinetic parameters of sarizotan will be calculated for each dose level (Dose Levels 1 and 4 only) using non-compartmental methods, e.g. C_{max} , t_{max} , $t_{1/2}$, $AUC_{(0-t)}$ and $AUC_{(0-\infty)}$. The derived pharmacokinetic parameters will be listed and plotted by subject and summarized by treatment. An analysis will be performed to evaluate the multiple-dose pharmacokinetics (PK) of sarizotan at the doses tested, and determine if the PK parameters are dose proportional.

15.2 Statistical methods

This is a prospective, 24-week, randomized, double-blind, placebo-controlled study, with a 168-week open-label extension, designed to evaluate the safety, tolerability, and efficacy of two oral doses of sarizotan in patients with RTT with respiratory abnormalities. At least 129 patients will be randomized (approximately 43/group) to receive 24 weeks of double-blind treatment with either low dose sarizotan [sarizotan 2 mg *bid* (age 4 to <13 years; or age \geq 13 years, weight <25 kg) or 5 mg *bid* (age \geq 13 years, weight \geq 25 kg)], high dose sarizotan [sarizotan 5 mg *bid* (age 4 to <13 years; or age \geq 13 years, weight <25 kg), or 10 mg *bid* (age \geq 13 years, weight \geq 25 kg)], or placebo *bid*.

At the start of the extension treatment period, all patients, including those previously randomized to placebo, will receive treatment with sarizotan and undergo dose titration, starting at a dose of 2 or 5 mg *bid*, dependent on age and body weight (see [Section 10.2](#)). The dose will be maintained at 2 mg *bid*, increased to 5 mg *bid*, or increased to 10 mg *bid* after 4 weeks if there are no tolerability issues.

Data from the initial 24-week double-blind period will be used for comparing the efficacy and safety of low dose sarizotan (2 and 5 mg *bid*) and high dose sarizotan (5 and 10 mg *bid*) vs. placebo. The data from the open-label extension period, during which all patients will receive sarizotan, will be analyzed separately to evaluate long-term effects of treatment. The Week 24 efficacy and safety assessments will serve as the baseline assessments for the extension treatment period.

15.2.1 Populations

The safety population will consist of all subjects who took a dose of study medication. The efficacy analyses will be performed on an Intent-to-Treat (ITT) population comprising all patients who were randomized to treatment.

15.2.2 Background and demographic characteristics

The background and demographic characteristics (age, race, ethnicity, weight, height, education, past and current medical conditions, etc.), disease characteristics, and prior/concomitant medication use for randomized patients will be summarized by treatment group. Continuous variables will be summarized by minimum, maximum, mean, median, and standard deviation, and discrete variables will be summarized using frequencies and percentages.

15.2.3 Study medication

The number of subjects receiving each dose level and the number of capsules taken will be reported.

15.2.4 Concomitant therapy

A listing of concomitant medications administered from the time of the first dose of the study medication through completion of the final (Week 192) evaluations will be summarized by treatment group for the double-blind period (Days 1-168), and overall for the open-label extension period (Days 169-1344).

15.2.5 Safety evaluations

All subjects who receive a dose of study medication will be included in the safety analyses. All adverse events will be listed and summarized by body system and preferred term. The incidence of AEs (%) and their relatedness to the study drug, as assessed by the Investigator, will be reported. Serious adverse events (SAEs) and events which are newly occurring or worsening after administration of the study medication (TEAEs) will be summarized. In addition, adverse events that result in death or discontinuation (ADOs) of the study medication will be listed separately.

Results for other safety parameters such as vital signs, laboratory parameters, ECGs, physical, neurological and ophthalmological examinations, and the suicidality assessment, will be listed and summarized accordingly. Changes from baseline in vital signs, ECG and laboratory values, and physical, neurological and ophthalmological examination findings will be summarized, with abnormal and clinically notable values/findings being identified. In the initial 24-week, double-blind, placebo-controlled period, a comparison will be made between the sarizotan and placebo groups in the proportion of subjects experiencing SAEs, ADOs, and TEAEs and any clinically significant abnormalities in other safety parameters. Where feasible, mean changes from baseline will be examined using a paired t-test. Safety data for the open-label extension period will be analyzed separately and will use the Week 24 evaluations from the double-blind period as the baseline assessments.

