The safety population will consist of all subjects who took at least one dose of study medication. All AEs will be summarized by body system and preferred term. The incidence (%) of SAEs, AEs that are newly occurring or worsened after administration of study medication (i.e. treatment-emergent AEs [TEAEs]), and AEs leading to discontinuation (ADOs) will also be summarized; severity of each AE and relatedness to study medication will be

assessed and presented. Changes from baseline in vital signs, ECG and laboratory values, and findings on physical, neurological and routine ophthalmology examinations will be summarized, with abnormal and clinically notable values/findings being identified. In the initial 24-week, double-blind, placebo-controlled period, a comparison will be made between the sarizotan and placebo groups in the proportion of patients experiencing SAEs, ADOs, TEAEs and any clinically significant abnormalities in other safety parameters. Where feasible, mean changes from baseline will be examined using a paired t-test. Safety data for the open-label extension period will be analyzed separately and will use the Week 24 evaluations from the double-blind period as the baseline assessments.

Efficacy Analysis:

Primary Efficacy Outcome. The primary efficacy analysis for the initial, 24-week, double-blind, treatment period will be performed on the Intent-to-Treat (ITT) population, consisting of all patients who were randomized to treatment. The percent reduction (change) from baseline in the number of apnea episodes (each ≥ 10 seconds in duration) per hour, during awake time, will be compared between treatment groups using a Mixed Model Repeated Measures (MMRM) analysis. The MMRM model will include percent change from baseline as response, the fixed, categorical effects of treatment group, visit, treatment group-by-visit interaction, and the continuous terms age and baseline value as covariate. A statistically significant difference between high dose sarizotan (5 or 10 mg *bid*) and placebo will be considered evidence of efficacy in reducing apnea.

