A randomized, double-blind study design will be used for the initial 24-week treatment period of this study to reduce potential bias in the assignment of patients to treatment and in the assessment of efficacy and safety parameters. A total of 129 patients will be included in this study, with approximately equal numbers of patients randomly assigned (1:1:1) to treatment with low dose sarizotan [2 mg *bid* (age 4 to <13 years; or age ≥13 years, weight <25 kg) or 5 mg *bid* (age ≥13 years, weight ≥25 kg)], high dose sarizotan [5 mg *bid* (age 4 to <13 years; or age ≥13 years, weight <25 kg), or 10 mg *bid* (age ≥13 years, weight ≥25 kg)], or placebo *bid*. The approximately equal randomization to each group allows for a drug-placebo comparison for safety and efficacy for each dose. Samples sizes were computed based on percent reductions of 20% and 10% between the sarizotan high dose and placebo groups, assuming an attrition rate of 25%, and a SD of 20 or 12.5, respectively. The sample sizes of 30 or 43 per group provides 90% power to detect a difference of -20% (-30% for sarizotan high dose vs. -10% for placebo) or -10% (-20% for sarizotan high dose vs. -10% for placebo) in the percent reduction in apnea episodes per hour (apnea index).

There are currently no approved treatments for respiratory abnormalities in RTT patients; therefore, a placebo control, rather than an active control, will be used in this study. The use of a device to record respiration as well as the structured method of observation may lead to learning effects. The placebo control has been included so that a background rate of spontaneous occurrence of adverse events, as well as changes in other safety and efficacy parameters, can be established in placebo-treated patients, against which the active treatment will be compared, without introducing a bias from knowledge of the treatment by the caregivers or investigators.

Amend. 1, 19Jan2016; Amend. 2, 18May2016; Amend. 3, 21Oct2016; Amend. 4, 03Mar2017; Amend. 5, 29Mar2017; Amend. 6, 13Apr2017; Amend. 7, 02Oct2017; Amend. 8, 02Nov2017; Amend. 9, 11Feb2018; Amend. 10, 29Nov2018; Amend. 13, 10Dec2019; Amendment 14, 17 March 2020, Clean, Final

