12.1.8 Tanner Staging

The sexual maturity of patients enrolled in the study will be evaluated at baseline and at Weeks 24, 48, 72, 96, 120, 144, 168 and 192 (or at early discontinuation) during the treatment period using the Tanner scale (Marshall and Tanner, 1969; Marshall and Tanner, 1970; see Appendix 7). The scale defines physical measurements of development in children, adolescents and adults based on external primary and secondary sex characteristics, such as the size of the breast, genitals, testicular volume and development of pubic hair. Due to natural variation, individuals pass through the Tanner stages at different rates, depending in particular on the timing of puberty. Tanner Staging will be used to assess potential effects of sarizotan on sexual development in the RTT patients.

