6. GENERAL CONSIDERATIONS

Descriptive statistics for continuous variables will be summarized by treatment group with n, mean, standard deviation (SD), median, minimum, and maximum, where appropriate. Descriptive statistics for categorical variables will be summarized by treatment group with count and percentages. All percentages should use the total number of subjects with data available in the relevant analysis set as the denominator, unless otherwise specified. Categories for missing data will be presented as appropriate.

Decimal places format

In general, the number of decimal places displayed for each statistic will be determined as follows, unless otherwise specified:

Descriptive Summaries	
Range (Min, Max)	Recorded decimal places
Mean, Median, Geometric Mean	Recorded decimal places + 1
Standard Deviation, Standard Error	Recorded decimal places + 2
Inferential Statistics	
LS Means, Difference in LS Means	Recorded decimal places + 1
CI's corresponding to LS Means and Difference in LS Means	Recorded decimal places + 2
Odds Ratio	Recorded decimal places + 3
Listings	Recorded decimal places

Percentages: All percentages between 0 and 99 will be rounded to one decimal unless there is a need to report more than one decimal for percentages (e.g., AEs).

P-values, if any, shall be reported to four decimal places or as <0.0001.

Data from subjects excluded from an analysis set will be included in the data listings, but not in the summaries.

Document: \\ieedc-vnasc01\BIOSdata\Newron\Sarizotan\PXA76395\Biostatistics\Documentation\SAP
 Author: [name] Version Number: V2
 Version Date: [30March2020]

Template No: CS_TP_BS016 – Revision 4
 Effective Date: 01Apr2016

Reference: CS_WI_BS005

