17.5. VITAL SIGNS

The following vital signs measurements will be reported for this study:

- Systolic Blood Pressure (mmHg)
- Diastolic Blood Pressure (mmHg)
- Pulse (bpm)
- Respiratory Rate (breaths/min)
- Body Temperature (⁰C)

The following summaries will be provided for vital signs data:

- Actual values and change from baseline by visits and timepoints
- Incidence of clinically notable vital signs values at Day 1, Day 15, Week 24 and End of Study visits as defined in Appendix 3 of the SAP
- Listing of patients' vital signs

The descriptive statistics for actual measurement and change from baseline will be presented by treatment group and timepoints at scheduled visits.

Document:	\\ieedc-vnasc01\BIOSdata\Newron\Sarizotan\PXA76395\Biostatistics\Documentation\SAP		
Author:	[name]	Version Number:	V2
		Version Date:	[30March2020]
Template No:	CS_TP_BS016 – Revision 4	Reference:	CS_WI_BS005
Effective Date:	01Apr2016		

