17.10. TANNER STAGING

A patient-wise listing of Tanner staging will be provided.

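### The protocol's only named safety test leaves out the placebo arm; the SAP drops it undeclared, adds no between-arm safety estimate, and only lists Tanner stage

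*Protocol*

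**What the plan says.** **Protocol.** Section 15.2.5 names a single test for safety: "Where feasible, mean changes from baseline will be examined using a paired t-test". The synopsis repeats it. Both places also promise a comparison of arms. Section 15.2.5 says "a comparison will be made between the sarizotan and placebo groups in the proportion of subjects experiencing SAEs, ADOs, and TEAEs", extended to clinically significant abnormalities in other safety parameters, and the synopsis says "a comparison will be made between the sarizotan and placebo groups in the proportion of patients experiencing SAEs, ADOs, TEAEs". Neither names a test, an effect measure or an interval. Section 7.3 explains why there is a placebo arm: it is there so that background adverse events and "changes in other safety and efficacy parameters, can be established in placebo-treated patients, against which the active treatment will be compared". Section 12.1.8 gives the purpose of one measure: "Tanner Staging will be used to assess potential effects of sarizotan on sexual development in the RTT patients".

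**SAP.** Section 6 sets the general format: "Descriptive statistics for continuous variables will be summarized by treatment group with n, mean, standard deviation (SD), median, minimum, and maximum". Section 8 fixes the table columns as low dose, high dose and placebo, with a further set for pooled sarizotan against placebo. Laboratory values (17.3) get change from baseline by arm, shift tables and the incidence of notable values. For vital signs (17.5), "The descriptive statistics for actual measurement and change from baseline will be presented by treatment group and timepoints at scheduled visits". The 17.5 list has blood pressure, pulse, respiratory rate and temperature. Weight appears only as a 7% flag in Appendix 3, and height does not appear. For sexual maturity, 17.10 says only "A patient-wise listing of Tanner staging will be provided". The paired t-test is nowhere in the SAP, and section 3.3 declares no change from the protocol.

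**The concern.** A paired t-test asks whether a value moved between two visits in the same patients. Whether it is run arm by arm or on pooled patients, placebo plays no part as a comparator. Enrolment starts at age 4 and the double-blind period lasts 24 weeks, so size, maturation and some laboratory values can be expected to move with no drug at all. A significant change on sarizotan beside a non-significant change on placebo is not evidence of a drug effect, and the opposite pattern is not reassurance.

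The SAP removes that test but puts no estimate in its place, so a reader of the report gets side-by-side columns and must judge the size and uncertainty of any difference by eye. Growth and maturation are where this matters most. The juvenile rat study in protocol 7.1.2 reports reduced ulnar growth and delayed reproductive maturity at the top dose, and weight-gain abnormalities and oestrus irregularity more widely. It also gives safety margins of 1 to 5 times predicted exposure. The protocol says most of these changes recovered, but it still set up Tanner staging to look for an effect, and the SAP gives that question no table by arm.

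**Working it through.** **Side by side**

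| Item | Protocol | SAP |
|---|---|---|
| Mean change, labs and vital signs | Paired t-test | Descriptive by arm; no test, difference or CI |
| Proportions with SAEs, ADOs, TEAEs | Arms to be compared; method not named | Counts and percentages; no difference or CI |
| Tanner stage | To assess effects on sexual development | Patient listing only |
| Weight and height | Measured as vital signs (12.1.2) | Weight as a 7% flag only; height absent |
| Declared departures | n/a | None (3.3) |

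SAP 6.4 says tests of treatment effects are against placebo at two-sided 0.05, but section 17 applies no test.

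**Arm sizes.** The documents give no figure for safety, so the sample size of the efficacy plan sets the scale. For a difference of 10 and SD of 12.5 (standardised 0.80), two-sided 0.05 and 90% power, the two-group t-test needs 33.83, so 34 per group (power 90.2%). The plan enrols 43 (34 × 1.25 = 42.5). I use both 43 and 34.

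**Illustration of the protocol's test.** Assumptions: zero drug effect, and the same 24-week drift *d* in every arm, in SDs of the change score. The documents give no drift, so a range is shown. The paired t statistic is then noncentral t with n − 1 degrees of freedom and noncentrality d√n. The critical values are 2.018 (n = 43) and 2.035 (n = 34).

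| Drift *d* | d√43 | P(significant), n = 43 | d√34 | P(significant), n = 34 |
|---|---|---|---|---|
| 0.2 | 1.311 | 24.9% | 1.166 | 20.5% |
| 0.3 | 1.967 | 48.5% | 1.749 | 39.7% |
| 0.5 | 3.279 | 89.3% | 2.915 | 80.8% |

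Each figure is the rate for one arm's own test. In a between-arm test the shared drift cancels and the rate is 5% whatever *d* is. With 20,000 simulated trials at *d* = 0.5 and 43 per arm, the paired test was significant in 89.6% and the two-sample test in 4.8%.

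**What between-arm intervals would deliver.** The half-width of the 95% CI for a difference in mean change, in SDs, is t × √(2/n):
- 43 v 43: 1.989 × 0.2157 = 0.43
- 34 v 34: 1.997 × 0.2425 = 0.48

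For a risk difference with 43 per arm, the half-width is 1.96 × √(2p(1 − p)/43). That is about 9, 13, 17 and 21 percentage points at event rates of 5%, 10%, 20% and 50%.

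**Chance exclusions of zero.** Protocol Table 7, the 11.4.1 test list and SAP 17.5 give about 42 quantitative measures: 10 haematology, 22 chemistry, 2 urine, 3 hormones and 5 vital signs. Weight and height make 44. With two contrasts each at one visit, 44 × 2 × 0.05 = 4.4 intervals would exclude zero with no drug effect.

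**The case against.** The strongest objection is that the SAP is the operative plan. Protocol 15.2.8 leaves the statistical detail to it, it runs no paired t-test, and its tables put a concurrent randomised placebo column beside each dose group and beside pooled sarizotan. This stands. For laboratory values, the listed vital signs and adverse events, the placebo column does allow for time and growth descriptively, and the rejection rates above describe a test that would not be produced under the current SAP.

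It is also true that the protocol promised a comparison of proportions without naming a method, so percentages by arm can be read as a descriptive form of it. Descriptive safety reporting is common at this sample size. The paired t-test itself was conditional on feasibility.

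On Tanner stage, protocol 15.2.5 does not list it among the parameters to be summarised, and SAP listings are organised by dose group and placebo. The double-blind period has only Baseline and Week 24 readings. Staging continues in the extension, which has a separate SAP. Cells in a shift table may be sparse. These points lower the yield of a table, but 12.1.8 sets a question about a drug effect, and the randomised comparison with placebo exists only in the double-blind period, where a listing does not answer it.

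Two sources cannot be seen: the ECG SAP, and the output templates to which SAP 17.1 refers for the adverse-event overview.

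**Conclusion.** The concern holds as a gap in specification and an undeclared difference between the two documents; it does not make the design invalid. Three things stand:
- The only safety test the protocol names confounds drug effect with growth and time.
- The SAP drops it while 3.3 declares no change, and specifies no between-arm difference or interval for any safety outcome in section 17.
- Tanner stage has no summary by arm despite its stated purpose, and height and mean weight change have none either.

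The 25% to 89% range (21% to 81% with 34 patients) applies to the protocol's test only. It rests on an assumed drift of 0.2 to 0.5 SD shared by the arms, with no drug effect.

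A reader might infer that safety will be reported without its control, or that drug effects cannot be separated from growth and time. The documents do not support that for laboratory values, the listed vital signs or adverse events, where placebo is tabulated alongside. What is missing there is the difference with its uncertainty. A reader might also multiply the paired-test error rates into a count of false alarms in the report. That does not follow, because the SAP runs no such test. Nothing is concluded about ECG.

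**What to change.** Before unblinding:

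- **Protocol 15.2.5 and synopsis:** delete the paired t-test sentence.
- **SAP 17.10:** add a Tanner shift table by arm, Baseline to Week 24, for patients below stage V at baseline. Split by age group only if cell counts allow.
- **SAP 17.3 and 17.5:** add high-minus-placebo and low-minus-placebo differences in change from baseline with 95% CIs, adjusted for baseline and age (the covariates SAP 7.1 already uses), without p-values. Add weight and height to the 17.5 list.
- **SAP 17.1:** add risk differences with 95% CIs for any TEAE, any SAE and any AE leading to discontinuation.
- **Labelling:** state that these intervals are descriptive and not adjusted for multiplicity.
- **SAP 3.3:** record the removal of the paired t-test and these additions.

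The cost is wording and a few more tables from data already collected. The downside is more output, with some intervals excluding zero by chance (about 4 of 88 under the count above), which is why the label matters.
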